9.4.3 ANALYSIS OF THE SECONDARY ENDPOINT(S)

Secondary Outcomes of Effectiveness Trial - The secondary outcomes are perceived access, quality of life and risk factors for premature mortality. **Access:** Perceived access to OUD services will be measured using a modified version of the 9-item SPIRIT Perceived Access Scale developed for our PCORI trial. The scale is based on theory,¹¹ has excellent internal consistency (κ - 0.89), and concurrent validity with number of mental health encounters ($p=0.016$). **PTSD symptoms** will be assessed using the PCL-5.⁶⁹ **Depression symptoms** will be assessed using the SCL-20.⁷⁰ **Anxiety** will be measured using the Neuro-QOL Measure - *Emotional Distress, Anxiety, Short Form 7a*.^{71,72} **Health Related Quality of Life** will be measured using the Veterans Short Form-12.⁷³ **Risk factors for premature mortality:** Risks, including suicidal ideation (two items from SCL-20), discontinuing MOUD⁶, overdose, suicide attempts, emergency department admission, hospitalization⁷⁴ and death, will be collected from participating clinics as part of the adverse event reporting process. Depending on their observed frequency, these risk factors will be analyzed separately or grouped.

Clinical Mechanism of Action (MOUD Persistence) - Patient self-report will be used to determine whether the patient engaged in MOUD, defined as the ratio of the number of days they reported taking the MOUD medication (numerator) to the number of days during the 6-month follow-up period for which it was prescribed (denominator).⁵¹

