Primary outcome. There are two primary outcomes (see Table 1). Opioid use is one of our primary outcomes and is measured using item 7E from the Brief Addiction Monitor-Revised (BAM-R) which was derived from the Addiction Severity Index35 by CESATE: “7. In the past 30 days, how many days did you use any of the following drugs: E. Opiates (e.g., Heroin, Morphine, Dilaudid, Demerol, Oxycontin, oxy, codeine (Tylenol 2,3,4), Percocet, Vicodin, fentanyl, etc.)?” Our other primary outcome is mental health related quality of life and is being measured using

the Veterans Short Form Health Survey 12 Mental Health Component Summary score (MCS). Both primary outcomes are assessed at the 6-month follow-up survey.

Secondary outcomes. This study includes 24 secondary outcomes, assessed at both the 3-month follow-up and the 6-month follow-up (Table 1). Secondary outcomes include the use of other drugs, depression, anxiety, PTSD, pain, physical health-related quality of life and perceived access to OUD care (see Table 1). Secondary outcomes also include opioid use and mental health related quality of life assessed at the 3-month follow-up survey. Exploratory outcomes are risk factors for premature mortality, including suicidal ideation, discontinuing MOUD, overdose, suicide attempts, emergency department admission, and hospitalization. Risk factors are collected via survey and adverse event reporting.

Construct/Instrument	Instrument(s)	Baseline	3-Month Follow-Up	6-Month Follow-Up
Multiple Primary Outcomes				
Opioid Use	BAM-R ^{1,2}	X	X	X
Mental health related quality of life (MCS)	Veterans Short Form-12 ³	X	X	X
Secondary Outcomes				
Pain	PEG ⁴	X	X	X
Alcohol Use	AUDIT-C ⁵	X	X	X
Cannabis Use	BAM-R ^{1,2}	X	X	X
Other Drug Use	BAM-R ^{1,2}	X	X	X
Depression	SCL-20 ⁶	X	X	X
Anxiety	PROMIS Measure - Anxiety, Short Form ^{7,8}	X	X	X
PTSD	PCL-5 ^{9,10}	X	X	X
Physical health related quality of life (PCS)	Veterans Short Form-12 ³	X	X	X
Access to Care	APAC ¹¹	X	X	X
Exploratory Outcomes				
Risk factors for mortality	WFS ¹ and Adverse Events	X	X	X
Mediator Variable				
MOUD Consistency	WFS ¹	X	X	X

APAC - Assessment of Perceived Access to Care

BAM-R - Brief Addiction Monitor-Revised

ICR - Individual Change Readiness

MOUD – Medications for Opioid Use Disorder

PCL-5 - PTSD Check List

PC-PTSD-5 – Primary Care PTSD Screen for DSM-5

PCS - Physical health related quality of life

PEG - Pain, Enjoyment of Life and General Activity

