4.1. Primary and Secondary Outcomes (Hypotheses 1 and 2)

Hypothesis 1: Compared to patients with MHS and OUD at clinics randomized to the control, patients at clinics randomized to the intervention group will report better access to and engagement in OUD treatment, less opioid use (primary outcome), better mental health functioning (primary outcome), fewer disorder specific mental health symptoms, better quality of life, and fewer risk factors for premature mortality (exploratory outcome).

All outcomes will be analyzed with a multilevel model accounting for clustering of observations (level 1) within patients (random effects at level 2) and clinics (random effects at level 3). The combined equation for the basic multilevel model applicable to a quantitative outcome such as mental health quality of life is as follows:

$$\begin{aligned} Y_{cit} = & \beta_0 + \beta_1(\text{Intervention}) + \beta_2(3 \text{ months}) + \beta_3(6 \text{ months}) \\ & + \beta_4(\text{Intervention} \times 3 \text{ months}) \\ & + \beta_5(\text{Intervention} \times 6 \text{ months}) + \beta_6 \text{DesignVars}_c \\ & + [u_c + u_{ci0}(\text{baseline}) + u_{ci3}(3 \text{ months}) + u_{ci6}(6 \text{ months})] \quad (\text{Eq. 1}) \end{aligned}$$

where c = clinic, i = patient, t = time

t_0 = baseline

t_3 = 3-month follow-up

$t_6 = 6$ -month follow-up

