Here the outcome measured at time t , for subject i , in clinic c is denoted by Y_{cit} . To account for the cluster-randomization this model includes a random effect for each clinic denoted as u_c . In order to allow a general longitudinal correlation and variance structure we use three subject-specific error terms denoted by u_{cit} for $t=0, 3, 6$ months. We assume a general 3×3 covariance model for these error terms to provide maximal validity to inference regarding change over time. To allow for potential non-linear change over time, we will enter time as a nominal variable by including dummy codes for the 3 and 6 month time points represented by the variables (3 months) and (6 months). Intervention main effects and interaction between intervention and time indicators capture the difference between intervention clinics and control clinics at each wave – with β_1 representing the adjusted mean difference across intervention groups at baseline (adjusting for the design variables) -- with $\beta_1 + \beta_4$ representing the adjusted mean difference across intervention groups at 3 months – and with $\beta_1 + \beta_5$ representing the adjusted mean difference across intervention groups at 6 months. Therefore, the primary contrasts are given by with β_4 as the 3-month intervention effect, and β_5 as the 6-month intervention effect. Note that each intervention effect accounts for the potential imbalance of outcomes across the intervention and control groups at baseline due to the small number of clusters (β_1) and this is removed from the cross-sectional mean contrasts at each follow-up time to define the key intervention effect parameters. *DesignVars* denotes a vector of covariates that includes: 1) low vs high fidelity, which must be controlled because it was a design/stratification variable for some clinics, and 2) additional covariates theoretically related to both the primary outcome and the probability of not completing follow-up surveys which will aid in enhancing validity against missing data and improving precision of estimation. Specifically, we will include: 1) worried about not have stable housing in the next two months, 2) being on parole or probation and/or presently awaiting charges, trial or sentencing, 3) opioid craving, 4) pain, 5) Audit-C, 6) provider trust (APAC item #6), and 7) any use of other drugs (dummy coding for each class of drug). The pre-specified primary effect of interest will be β_5 , which represents the difference in change from baseline between intervention and control clinics at 6 months. Table S2 presents a shell table for the primary outcome and Figure 2 presents a shell plot. Table S3 presents a shell table for the secondary outcomes.

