
For the primary outcome (mental health related quality of life [0-100]) we will use a linear mixed model with a normal distribution with a linear link function and model structure given above in Equation 1. For the primary outcome days-using-opioids [0-30] we will modify the above linear mixed model and adopt a similar regression structure using a generalized linear mixed model with binomial distribution logit link function. We will retain the random effect structure to include a random effect for clinic and include the time-specific subject-level error terms to both allow for binomial overdispersion and a general longitudinal covariance over time. For the secondary and exploratory outcomes, appropriate link functions will be used for linear, binary (logit), ordinal (logit), and count (Poisson/negative binomial depending on dispersion) data. For any binary longitudinal outcomes, we will simplify the subject-level random effects to be a simple random intercept due to identifiability (no overdispersion and only correlation).

Effect sizes. Cohen's d effect sizes will be calculated and presented with 95% confidence intervals. Between group effect sizes will be calculated as the model-estimated treatment effect at each time point divided by the pooled, raw baseline standard deviation.

Testing of Multiple Primary Outcomes. The intervention will be interpreted to have been successful if there is a significance group difference between either primary outcome, not necessarily both primary outcomes. Corrections for multiple testing will be computed using a Bonferroni correction for the two multiple primary outcomes and therefore we will use an $\alpha=0.05/2 = 0.025$ to test each primary outcome. All secondary outcomes are exploratory and no multiple testing adjustment will be used. We will present secondary and exploratory outcomes descriptively using a forest plot to illustrate the collection of associations with intervention.

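### SAP 4.1 puts several secondary outcomes among their own covariates: the pain model then has no maximum likelihood fit, and the drug-use models are circular

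*SAP*

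**What the plan says.** SAP 4.1 opens with one model for everything: "All outcomes will be analyzed with a multilevel model accounting for clustering of observations (level 1) within patients" and clinics. Equation 1 has responses at 0, 3 and 6 months and a DesignVars term whose coefficient does not vary with time. On the covariance it says: "In order to allow a general longitudinal correlation and variance structure we use three subject-specific error terms", with a general 3×3 covariance matrix.

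Besides fidelity, DesignVars holds "additional covariates theoretically related to both the primary outcome and the probability of not completing follow-up surveys". These include "4) pain, 5) Audit-C, 6) provider trust (APAC item #6), and 7) any use of other drugs", with a dummy variable for each drug class. No measurement time is given.

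SAP section 3 states: "Secondary outcomes include the use of other drugs, depression, anxiety, PTSD, pain, physical health-related quality of life and perceived access to OUD care". Its Table 1 also lists AUDIT-C and cannabis as secondary outcomes. Shell Table S3 gives pain, AUDIT-C, cannabis, other drugs and the access scale a baseline row each.

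Only two changes to the model are stated for secondary outcomes. One is the link: "For the secondary and exploratory outcomes, appropriate link functions will be used for linear, binary (logit), ordinal (logit), and count" data. The other is the random effects: "For any binary longitudinal outcomes, we will simplify the subject-level random effects to be a simple random intercept due to identifiability". SAP section 5 specifies maximum likelihood estimation.

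**The concern.** Read as written, the pain model has baseline PEG on the left-hand side of the baseline row and baseline PEG again on the right. The cannabis, other-drug and AUDIT-C models repeat the pattern, and the access model does so in part. This is a stated rule that breaks down when applied, not merely a detail left open. SAP 4.1 says the covariates are there to protect against missing data and improve precision. For these outcomes they can do the opposite: no converged fit or an arbitrary one for pain, and a baseline contrast with no useful meaning for drug use. The analyst would then have to choose a repair after seeing the data.

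**Working it through.** The documents give no figure on this point, so the check is whether the models are identified.

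**Inputs.** 254 patients and 28 enrolling clinics (SAP section 6); Equation 1, the covariate list and the link rules (SAP 4.1); outcome panels (Table S3). All variances, effects and dropout patterns below are assumptions.

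**Pain, algebra.** Table S3 reports PEG as an adjusted B with Cohen's d, so a linear model is assumed. Set the clinic variance to zero and let g be the coefficient on own baseline. The baseline residual is

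Y0 − β0 − β1·A − g·Y0 = (1 − g)·(Y0 − m − d·A), with m = β0/(1 − g), d = β1/(1 − g), and A the arm.

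Its SD is (1 − g) times the ordinary baseline SD. The free covariance lets the follow-up rows be matched exactly with β5 unchanged. Hence, for any g below 1,

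log L(with own baseline) = log L(without) − n·ln(1 − g).

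With n = 254:
- g = 0.9: gain 254 × ln(10) = 584.9
- g = 0.99: gain 254 × ln(100) = 1,169.7
- g = 0.999: gain 254 × ln(1,000) = 1,754.6

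The gain has no upper limit. Zero clinic variance is an allowed value, so the full model's likelihood is unbounded too.

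**Pain, numerical check.** One simulated PEG-like dataset (three waves, clinic SD 0.3), with the baseline residual SD held at falling values:

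| Baseline residual SD | Log-likelihood | Own-baseline coefficient | β1 | β5 | SE of β5 |
|---|---|---|---|---|---|
| 1 | −1328.2 | 0.929 | 0.0054 | −0.7288 | 0.805 |
| 0.1 | −744.7 | 0.992 | 0.0006 | −0.7288 | 0.701 |
| 0.01 | −163.1 | 0.9992 | 0.0001 | −0.7288 | 0.690 |
| 0.001 | +379.6 | 0.9999 | 0.0000 | −0.7288 | 0.519 |

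The steps are 583.5, 581.6 and 542.7, against 584.9 in theory; the search was bounded and capped at 25 iterations. The SEs depend on where the search stops. The fitted clinic SD fell to about 0.001, the lower limit of the search, so clustering effectively left the model. Without own baseline there is a proper maximum: log-likelihood −1679.2, β5 = −0.729 (SE 0.321), equal to the raw difference in change.

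**Cannabis and other drugs.** Random-intercept logit, 60 simulated trials per scenario, complete data. Every fit was finite, with an own-baseline coefficient of about 3.0 (largest 4.0). Medians without and with own baseline:
- β5: 0.02 and 0.02 (true 0); −0.88 and about −0.88 (true −0.8)
- random-intercept SD: about 2.0 and about 0.6 (true 2)
- β1, when truly 1.0: 0.43 with own baseline

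**AUDIT-C.** Table S3 places it in the odds-ratio panel, so the zero-residual argument does not carry over. If modelled as linear it would fail as PEG does (by the same algebra; not simulated).

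**Access.** The covariate is one item of what Protocol 9.4.3 calls a "modified version of the 9-item SPIRIT Perceived Access Scale". One item does not equal the scale, so the baseline row is not fitted exactly and the likelihood stays bounded (algebra, not simulated).

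**Dropout.** These simulations make dropout of about 20% depend on baseline in opposite directions by arm, a deliberately unfavourable pattern. Protocol 9.2 allows for 20% attrition.
- PEG: by the identity above, β5 keeps its usual value for any g below 1. At the boundary itself, with a slope of exactly 1 on baseline, the fit becomes a comparison of change scores in completers. There the bias was 0.07 to 0.61 points in size in one set of two-wave simulations (dropout 17–21%, correlations 0.3–0.7, SD 2.5) and 0.23 to 0.47 in another. Without own baseline it was about 0.
- Binary: β5 moved from −0.69 to −0.43 when own baseline was included, that is, from an odds ratio of exp(−0.69) = 0.50 to exp(−0.43) = 0.65. β1 fell from about 0.4 to 0.16 and the random-intercept SD from 2.0 to about 0.45.

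**The case against.** The best defence is that the list was never meant to carry over unchanged. It is justified by relation to the primary outcome. SAP 4.2 says explicitly that the moderation analysis uses the primary outcome's design variables, and 4.1 has no such sentence for secondary outcomes. Protocol 9.4.3 ties covariates to the dependent variable. This shows that the authors may have intended something else, but it does not supply another rule: Equation 1 contains DesignVars, is introduced for all outcomes, and no other list is given.

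The second defence is that β5, the effect of interest, does not move. With complete data that is right, and it limits the harm. It does not rescue the standard errors or β1 for pain, nor β5 under the dropout pattern above. That pattern is unfavourable by design and shows what can happen, not what is likely.

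Third, SAP 4.1 calls all secondary outcomes exploratory, and an analyst would notice a failed pain model at once. That stands for pain. The binary models converge normally and would give no such warning.

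A reader might infer that all five overlapping constructs, of the nine secondary constructs in Table 1, lack a valid fit. The documents do not support this: exact failure follows for pain only, and for AUDIT-C only under a linear model. A reader might also take the removal of recent overdose for convergence, in the SAP's change log, as evidence of the same fault. Recent overdose is not one of the overlapping covariates, and nothing links that change to this mechanism.

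**Conclusion.** The rule in SAP 4.1 does not work for the outcomes that appear in its own covariate list. For pain no maximum likelihood fit exists, given a linear model and the unstructured covariance. For cannabis and other drugs the model can be fitted but is circular: in simulation the random-intercept SD fell from about 2.0 to 0.6 and a baseline contrast of 1.0 became 0.43. AUDIT-C depends on its link, and access overlaps by one item.

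The 6-month effect is essentially unchanged with complete data. Under dropout that depends on baseline in opposite directions by arm it can be biased; for pain this applies to a fit that settles at the slope-1 boundary. These sizes rest on assumed variances, effects and dropout.

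That the covariates are baseline values is itself an inference. If they were time-varying, PEG would equal its covariate at every wave, which is worse.

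It would be wrong to read this as a threat to the main result. Neither opioid days nor the MCS is in the covariate list, so the primary analyses are unaffected.

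**What to change.** Add to SAP 4.1 that the additional covariates are baseline values, and that any covariate that is, or is an item of, the outcome being modelled is dropped from DesignVars in that outcome's model. This means PEG for pain, AUDIT-C for alcohol, the matching drug class (or each class within a combined outcome) for drug use, and APAC item #6 for access. Leave the primary-outcome model as it is.

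The cost is slightly different covariate sets across secondary outcomes, which a table footnote can state. No new data are needed.

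Taking baseline out of the response for every outcome would also remove the overlap, but it should not be done. It would replace the pre-specified difference in change from baseline for two primary outcomes that have no defect.

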The DSMB directed the research team to discontinue consenting new patients into the trial for reasons of futility due to the current rate of recruitment. Therefore, we present a revised power analysis calculated before the outcome data are to be unmasked. The revised power analysis is based on the observed number of patients enrolled (n=254), observed number of clinics enrolling ≥ 1 patient (n=28), the observed coefficient of variation (0.97) which represents the variation in cluster sizes, and the Intraclass Correlation Coefficients (ICCs) estimated for interim analysis requested by the DSMB. For the masked interim ICC estimation we used all patient data available on 11/7/2022, including N=191 in the baseline sample and N=155 in the 6-month follow-up sample. We adjusted for treatment group and baseline primary outcomes. We used the jackknife method to compute a standard error by computing ICCs deleting each cluster in turn and then averaging these estimates.¹⁶ For the 6-month follow-up, the opioid use ICC was estimated to be 0.00 (SE= 0.02). For the 6-month follow-up, and the MCS ICC was estimated to be 0.03 (SE=0.09). Based on these estimates, and using a Bonferroni correction to account for multiple outcomes, we will have 80% power to detect a medium effect size of 0.40 for days of opioid use and a medium effect size of 0.46 for MCS. This represents a difference of 2.65 (e.g., 15.00 days compared to 12.3 days) days using opioids and a difference of 6.22 (e.g., 40 compared to 33.8) on the MCS between the intervention and control groups.

7. References

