	Overall n (%) or μ (SD)	Intervention Group n (%) or μ (SD)	Control Group n (%) or μ (SD)
Age (years)			
Are you of Hispanic, Latino/a/e or Spanish origin?			
Yes			
No			
Missing			
Race			
American Indian, Alaska Native, or other Indigenous group			
Native Hawaiian or other Pacific Islander			
African American or Black			
White			
Multi-race			
Another Identity			
Missing			
Current Gender Identity			
Man			
Woman			
Non-binary or gender fluid			
Missing			
Marital Status			
Divorced			
Married or living with a partner			
Separated			
Single, never married			

Missing

Housing Status

No, not living in stable housing

Yes, living in stable housing

Missing

Concern about Future Housing

No, not worried about housing in the near future

Yes, worried about housing in the near future

Missing

Parole/Probation

No

Yes

Missing

Awaiting charges, trial, or sentencing

No

Yes

Missing

Currently mandated by a court to receive addiction treatment

No

Yes

Missing

Individual Readiness to Change (ICR; range: 0-10)

Importance for change

Confidence for change

Readiness for change

Clinical Characteristics:

Veterans Short Form 12 Mental Health Component Summary score

(MCS; range: 0-100)

Opioid Use:

Any opioid use in the past 30 days

Number of days of opioid use in the past 30 days

Opioid Craving:

Not at all

Slightly

Moderately

Considerably

Extremely

Medication for OUD:

Lifetime

Current

Alcohol Use: (AUDIT-C; range: 0-12)

Other Drug Use: Any use in the past 30 days

Cocaine and/or crack use

Other stimulant use

Sedative and/or tranquilizer use

Cannabis use

Inhalant use

Other illegal drug use

Recent Overdose Experience

Ever overdosed

Number of previous overdoses

Overdosed in the past 6 months

Number of overdoses in the past 6 months

Pain Level (PEG; range: 0-10)

Hopkins Symptoms Checklist (SCL-20; range: 0-4)

Anxiety (PROMIS Measure - Anxiety 8a - Adult v1.0: range: 36.4-76.8)

PTSD Checklist (PCL-5; range: 0-80)

Table S2. Multiple primary outcomes across intervention conditions

	Intervention		Control		Treatment Effects		
	Mean (SD)	95% CI	Mean (SD)	95% CI	Adjusted Odds Ratio	95% CI	Cohen's d
Opioid Use							
Baseline							
3 months							
6 months (primary outcome)							
					Adjusted Mean Difference	95% CI	Cohen's d
MCS							
Baseline							
3 months							
6 months (primary outcome)							

Table S3. Treatment effects for secondary and exploratory outcomes at 3 and 6 month follow-up

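### SAP section 6 does not establish 80% power for the primary contrast β5, and Table S2 does not say that β5 is the effect it will print

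*SAP*

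**What the plan says.** SAP section 4.1 fits one longitudinal model (Eq. 1) with an intervention main effect β1 and intervention-by-time terms β4 (3 months) and β5 (6 months). It describes β1+β5 as "representing the adjusted mean difference across intervention groups at 6 months". It then says that the baseline part β1 is "removed from the cross-sectional mean contrasts at each follow-up time to define the key intervention effect parameters", and pre-specifies β5, "which represents the difference in change from baseline between intervention and control clinics at 6 months". Each primary outcome is tested at alpha 0.025.

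Table S2 (SAP section 8) places the primary result in the row "6 months (primary outcome"), below a baseline and a 3-month row. The effect column is "Adjusted Mean Difference" for MCS and "Adjusted Odds Ratio" for opioid use, both under a general header for treatment effects. No coefficient is named. The effect-size paragraph of section 4.1 defines Cohen's d as the "model-estimated treatment effect at each time point divided by the pooled, raw baseline standard deviation".

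SAP section 6 states that "we will have 80% power to detect a medium effect size of 0.40 for days of opioid use", and 0.46 for MCS. Its listed inputs are 254 patients, 28 clinics, a cluster-size coefficient of variation of 0.97, and 6-month ICCs of 0.00 (opioid use) and 0.03 (MCS), estimated after adjustment for treatment group and baseline outcome. It illustrates the effects as differences between group levels: 15.00 against 12.3 days, and 40 against 33.8 MCS points.

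**The concern.** A pre-specified contrast has to carry through to the power statement and to the table that reports it.

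- **Power.** The variance of a difference in change depends on r, the correlation between a patient's baseline and 6-month values, and on how many patients have a 6-month value. Section 6 gives no value for r and lists no attrition allowance, so its 80% cannot be taken as the power of the β5 test. This matters most when a null result is read: a reader will rely on section 6 to judge which effects the trial could have missed.
- **Reporting.** In section 4.1's own vocabulary, an adjusted mean difference at 6 months is β1+β5. If Table S2 were filled in on that reading, the printed estimate, confidence interval and Cohen's d would differ from the pre-specified test by β1. Section 4.1 itself expects that β1 may not be zero with few clinics.

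**Working it through.** **Inputs.** From SAP section 6: N = 254, 28 clinics (mean size 254/28 = 9.07), CV 0.97, ICC 0.00 and 0.03, and 155 of 191 with 6-month data. From SAP section 4.1: alpha 0.025. Tests are two-sided (Protocol 9.4.2). Assumed, because the documents do not give it: r = 0.3, 0.5, 0.7. Effects are in SD units. Opioid days are treated as continuous, which approximates the binomial-logit model.

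**Step 1: reproduce the stated figures as a 6-month comparison.** With z = 2.241 + 0.842 = 3.083 and design effect DE, the detectable effect is d = 3.083 × 2 × √(DE/254).

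- Opioid use, ICC 0, DE = 1: d = 0.387 (0.407 with t on 26 df). This brackets 0.40.
- MCS, ICC 0.03, equal clusters: DE = 1 + 8.07 × 0.03 = 1.24, d = 0.43. With the CV: DE = 1 + (1.9409 × 9.07 − 1) × 0.03 = 1.50, d = 0.47 (0.50 with t). This brackets 0.46.
- Generalised least squares for Eq. 1 with simulated clinic sizes at CV 0.97 and ICC 0.03 gives about 0.46 for β1+β5 at every r tried.

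For β5 under Eq. 1 the shared clinic intercept almost cancels. At r = 0.5, moving the ICC from 0 to 0.03 takes the detectable effect from 0.387 to 0.381. The stated rise from 0.40 to 0.46 therefore fits a 6-month contrast and does not fit β5.

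**Step 2: power of β5, opioid use, ICC 0.** With n = 127 per arm and n₆ = 127 × 155/191 = 103 followed at 6 months:

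- complete data: Var(β5) = 4(1 − r)/n
- 81% follow-up: Var(β5) = 2[(1 − r²)/n₆ + (1 − r)²/n]
- power = Φ(0.40/√Var − 2.241)

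| r | Var, complete | Power | Var, 81% | Power |
|---|---|---|---|---|
| 0.3 | 0.0220 | 67% | 0.0254 | 61% |
| 0.5 | 0.0157 | 83% | 0.0185 | 76% |
| 0.7 | 0.0094 | 97% | 0.0113 | 94% |

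Generalised least squares with unequal clinics and arms gives 60%, 75% and 93% at 81% follow-up, and t on 26 df gives 56%, 71% and 91%. By the normal approximation, 80% power needs r of about 0.47 with complete data and 0.55 with 81% follow-up. At 81% follow-up the detectable effect is 0.49, 0.42 and 0.33 SD. The SD implied by section 6 is 2.65/0.40 = 6.6 days, so these are about 3.2, 2.8 and 2.2 days against the stated 2.65.

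**Step 3: power of β5, MCS at 0.46, 81% follow-up** (generalised least squares, normal approximation).

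| r | ICC 0.03 as a constant clinic effect (Eq. 1) | ICC 0.03 as clinic-by-time variation |
|---|---|---|
| 0.3 | 74% | 55% |
| 0.5 | 87% | 64% |
| 0.7 | 98% | 79% |

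The simulated clinic sizes move these figures by a point or two. Both columns are needed because the ICC was estimated at 6 months after adjustment for baseline. It may describe clinic variation that arises during follow-up, which does not cancel from a change.

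**Step 4: how far β5 and β1+β5 can differ.** Without covariates the standard error of β1 is 2/√254 = 0.126 SD at ICC 0 and about 0.150 SD at ICC 0.03. That is about 0.126 × 6.6 = 0.8 opioid days, or 0.150 × 13.5 = 2.0 MCS points (SD 6.22/0.46 = 13.5). The model's covariates would reduce this.

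**The case against.** **On reporting.** Section 4.1 names β4 and β5 as the 3- and 6-month intervention effects and introduces Table S2 as the primary-outcome shell in the same paragraph, so the table's treatment-effects header can fairly be read as β4 and β5. The baseline row is needed in any case for the group means. A reader might infer that Table S2 contradicts the model, or that the primary test is in doubt. The documents support neither: section 4.1 fixes one test, and no passage proposes a test of β1+β5. The protocol's description of differences at each wave (9.4.2) is no conflict either, because the SAP uses the same description before defining its contrast. What stands is a missing definition, most clearly for the opioid odds ratio.

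**On power.** Section 6 names no target parameter. At r = 0.5, ICC 0 and complete data, β5 has the same detectable effect (0.387) as the plain comparison, so 0.40 alone does not show which contrast was meant. The inference rests on the absent r and on the rise with the ICC. A reader might go further and conclude that the trial is underpowered. The documents do not show that, since at high r power can exceed 80%. The 81% is a lower bound on follow-up if some of the 191 were not yet due at the interim date. An allowance is nevertheless in keeping with the protocol, which assumed 20% attrition (section 9.2). Enrolment had already been stopped, so a restatement changes no design decision; its value is in interpretation.

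**Conclusion.** The concern holds as a mismatch of the power statement and the reporting shell with a sound primary contrast. The power part is the firmer one: 80% at 0.40 and 0.46 is not established for β5. For opioid use it holds only above an unstated r of about one half. For MCS it also depends on an unstated reading of the ICC. These results assume r, a linear approximation for opioid days, the normal approximation, no covariates, and data missing at random.

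The reporting part is an ambiguity whose possible effect is a printed estimate that differs from the tested one by β1. The point is minor to moderate: it should be corrected, but it does not threaten the validity of the primary test.

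**What to change.** 1. **Section 6.** Keep β5 as primary. Restate power, or the detectable effect, for β5 over a stated range of r and the expected 6-month follow-up, and say whether the ICC is taken as constant over time or as clinic-by-time variation.
2. **Tables S2 and S3 and the Cohen's d paragraph.** State that the 3- and 6-month effects are β4 and β5, and for opioid use exp(β4) and exp(β5), which are ratios of odds ratios. Relabel the MCS column, for example *Adjusted difference in change from baseline*. The printed estimate and interval are then those of the pre-specified test.

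The cost is a short power paragraph, a footnote and a column label. The restated power will look less favourable at low r. The model and the test stay as they are.
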